10.1.1 Withdrawn

Patients who withdraw their consent at any point in the study fall into one of two categories.

Site staff should ascertain which category a patient wishes to be in at the point of withdrawal;

- a) Those who allow their data (collected up to the point of withdrawal) to be used

OR

- b) Those who do not allow the use of any of their data collected prior to withdrawal.

10.1.2 Lost to follow-up

These are patients who do not attend a follow-up assessment after site staff have attempted to contact the patient at least twice, e.g. by telephone.

As these patients have not withdrawn their consent, the data already collected for them may be used and therefore needs returning in the usual manner.

10.1.3 Patients that have died

These patients have not withdrawn their consent and therefore the data already collected for them may be used.

10.2 Patients not lost

Patients that fall into one or more of the following categories, which are indications for treatment discontinuation, are not considered as withdrawn or lost from the study. They should continue to attend all follow-up study assessments as per protocol, unless they subsequently fall into one of the categories listed in Section 10.1;

- Patients who ask to stop study treatment
- Pregnancy
- Steroid psychosis or persisting psychotic symptoms for more than 7 days, that cannot be explained by alcohol withdrawal
- Any event which in the judgement of the PI makes further study treatment inadvisable
- SAE requiring discontinuation of treatment.

Stopping treatment or having a prolonged/numerous treatment gaps, for whatever reason, does not mean the patients are withdrawn or lost from the study, they should still continue to attend all follow-up assessments. If the screening biopsy histology is negative then the patient will be discontinued from the study, will not undergo any further treatment or the second biopsy but will be followed-up for safety assessment for 28 days, as per assessment schedule.

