1.7 Treatment, formulation, route of administration and dose

Consenting eligible patients will be included, randomized and treated before the histology result is available because histology results usually come back within 5 to 7 days depending on the hospital. If the histology is negative then the patient will be discontinued from the study, will not undergo any further treatment or the second biopsy and will not be included into the efficacy analysis but will be followed up for safety assessment. For each patient with a negative histology, another patient will be recruited to ensure that the sample of positive histology patients is 52. Additionally, recruitment will be continued until both biopsies (at Baseline and Day28) from 48 patients will be collected.

A single dose of 3 mg/kg canakinumab or identical placebo will be administered intravenously at baseline (Day 1). Canakinumab will be made up by dilution in 100 ml 5% Dextrose by an unblinded research personnel at each site.

Patients with AST >2 x ULN on Day 28 will receive a second dose of 3 mg/kg study drug administered i.v. on Day 28:

- Patients who received placebo on baseline will receive placebo.
- Patients who received canakinumab on baseline will receive canakinumab.

2 Background and rationale

Alcohol consumption causes a spectrum of liver abnormalities and leads to over 2 million deaths per year (1). Alcoholic hepatitis (AH) is a florid presentation of alcoholic liver disease characterized by liver failure (jaundice and coagulopathy) in the context of recent and heavy alcohol consumption (2). The condition carries a high fatality risk; patients with severe AH have a 30% mortality rate at 90 days after presentation. Moderate AH carries a mortality rate of 6-10% at 90 days. Currently there are no effective treatments for alcoholic hepatitis although clinical guidelines currently recommend prednisolone(3). Prednisolone therapy improves survival in patients with severe AH up to 28 days but beyond this timepoint a higher incidence of infection results in no survival advantage at 90 days compared to placebo treatment (4-6)

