3.5. Design

Multicentre, double blind, randomized (1:1), placebo controlled trial. The trial will follow patients up for 90 days and will be conducted in centres across the United Kingdom. Twenty-six patients will be recruited to each arm of the trial: total 52 patients.

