3.6. Treatment

Patients will be included and randomized and treated before histology result is available. If the histology is negative then patient will be withdrawn.

A single dose of 3 mg/kg Canakinumab or identical placebo will be administered intravenously at baseline (Day 1). Canakinumab will be made up by dilution in 100 ml 5% Dextrose by an unblinded research personnel at each site. The drug or placebo (5% Dextrose alone) will be labelled by the designated unblinded team member.

Patients with moderate to severe ascites should undergo large volume paracentesis prior to administration of Canakinumab.

Patients with AST >2 x ULN on Day 28 will receive a second dose of 3 mg/kg study drug administered i.v. on Day 28:

- Patients who received placebo on baseline will receive placebo.
- Patients who received canakinumab on baseline will receive canakinumab.

The second dose of study drug (or placebo) should not be administered if the patient experienced an incident of infection during the prior 28 days, MELD >27 or in cases where the PI is concerned about the patient's condition deteriorating.

Randomisation will be via the trial InForm database which will enable the unblinded research team to ensure the right dosing and drug preparation in respect of the AST assessment on D28.

4. Patient population

The trial will be conducted in patients with severe alcoholic hepatitis (mDF* ≥ 32 and MELD ≤ 27) with treatment initiated during an index hospital admission with the condition.

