7.5 Schedule of Assessments

Table 1 lists all of the assessments and indicates with an ‘x’ at which visits the assessments are performed. Patients should be seen for all visits on the designated day, or as close to it as possible – the visit window/tolerance for each visit is given below the table. At a minimum, patients will be contacted for safety evaluations during the 90 days following randomisation to the study. At this final visit the adverse event and concomitant medications should be reconciled on the CRF. Documentation of attempts to contact the patient should be recorded in the source documentation.

Table 1: Assessment schedule

| | Screening | Baseline 6, 9, 11 | Day 7 ⁴ | Day 14 ⁴ | Day 21 ⁴ | Day 28 ^{2, 11} | Day 42 ^{1, 4} | On Discharge ¹⁰ | Day 90 ³ | Unscheduled |
|--|----------------|----------------------|--------------------|---------------------|---------------------|-------------------------|------------------------|----------------------------|---------------------|-------------|
| Informed Consent | X | | | | | | | | | |
| Demographic data | X | | | | | | | | | |
| Inclusion/Exclusion criteria | X | X | | | | | | | | |
| HIV test [^] | X | | | | | | | | | |
| Pregnancy test ⁺ | X ⁵ | | | | | | | | X | |
| Hepatitis B & C serology[^] | X | | | | | | | | | |
| Genetic sequencing (PNPLA3) | X | | | | | | | | | |
| Urinary ethyl glucuronide | X | X | | | | X | X | | X | |
| Alcohol consumption | X | | | | | X | X | | X | |
| Duration since admission to hospital | | | X | | | | | | X | |
| Medical history | X | | | | | | | | | |
| Prior/Concomitant medications | X | X | X | X | X | X | X | X | X | |
| Vital signs | X | X | X | X | X | X | X | X | X | X |
| Physical exam | X | X | X | X | X | X | X | X | X | |
| Weight | X | | | | | X ¹ | | X | X | |
| Height | X | | | | | | | | | |
| Calorie and protein intake | | X | X | X | X | X | X | X | X | |
| Randomisation | | X | | | | | | | | |
| IMP / placebo administration | | X | | | | X | | | | |
| Prothrombin time | X | X | X | X | X | X | X | X | X | |
| Haematology [%] | X | X | X | X | X | X | X | X | X | X |
| Clinical chemistry [%] | X | X | X | X | X | X | X | X | X | X |
| Serum CK18-M30/M65 sample | | X | X | X | X | X | X | X | X | |
| DF, MELD, GAHS scores | X | X | X | X | X | X | X | X | X | |
| Lille score | | | X | | | | | | | |
| Overt GI Haemorrhage assessment [§] | X | X | X | X | X | X | X | X | X | |

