8.1 Power calculation

It is estimated that improvement of histological alcoholic steatohepatitis will occur in 40% of patients treated with placebo and 80% of patients treated with Canakinumab. A trial with 80% power to detect a difference at the $P < 0.05$ threshold would require 23 patients in each arm, 46 in total. Assuming a drop-out rate of 10%, we will recruit 52 patients in total (26 patients per group). Patients will be included and randomized and treated before histology result is available. If the histology is negative, then patient will be withdrawn and another patient recruited. Additionally, to meet the study power we will continue recruitment until we have paired biopsies in 48 patients.

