10.1 Patients lost

The following 3 sub-sections describe patients that will be regarded as having been lost from the study, i.e. no further follow-up visits will take place and no further data will be collected;

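### Dosed patients with negative histology have no single safety follow-up rule, so their Day 29–90 safety data may be incomplete

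*Combined protocol and SAP*

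**What the plan says.** Patients are "included, randomized and treated before the histology result is available" (Section 1.7). Anyone whose baseline biopsy proves negative has therefore already received canakinumab or placebo. Each such patient is replaced, so they come on top of the 52 patients with positive histology.

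What happens to them next depends on the section:

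- **1.7:** they are discontinued, "will not be included into the efficacy analysis but will be followed up for safety assessment". No length is given.
- **3.6:** "If the histology is negative then patient will be withdrawn". Follow-up is not mentioned.
- **8.1:** "If the histology is negative, then patient will be withdrawn and another patient recruited". Follow-up is again not mentioned.
- **10.2, on patients not regarded as lost:** they are to be "followed-up for safety assessment for 28 days, as per assessment schedule".
- **7.5, which holds that schedule:** "At a minimum, patients will be contacted for safety evaluations during the 90 days following randomisation to the study". No exception is made for negative histology. Section 3.5 likewise says: "The trial will follow patients up for 90 days".

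For patients counted as lost, Section 10.1 says that "no further follow-up visits will take place and no further data will be collected". Withdrawn patients are one of its three categories, and 10.1.1 describes them as patients who withdraw consent.

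Section 3.3 lists mortality at Day 90, and infection and sepsis, acute kidney injury and hepatic complications over 90 days. Under Section 9.5, routine reporting of serious adverse events ends at the patient's last study visit. After that, only deaths or events that may reasonably be related to the study are notified. Section 8.2 leaves secondary analyses and missing-data methods to a statistical analysis plan still to be written. The text defines no safety population.

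**The concern.** A safety analysis should account for everyone who received study drug. Two sites could treat the same dosed patient differently, depending on whether they work from 3.6, 10.2 or 7.5. Section 10.2 adds to the difficulty. It says that stopping treatment for any reason leaves a patient in all follow-up, then in the next sentence limits negative-histology patients to 28 days, citing a schedule that runs to Day 90.

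The period at issue is one that the protocol itself treats as informative. Its background (Section 2) says that prednisolone's survival benefit lasts to Day 28, and that a higher incidence of infection beyond then removes it by Day 90. Section 2.5 accepts that canakinumab may raise the risk of infection.

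If follow-up stops at Day 28 and these patients sit in the denominator of a simple 90-day proportion, the event rate is understated. If they are left out, exposed patients drop out of the safety result. With 26 patients planned per arm, a few exposures either way are noticeable.

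**Working it through.** **1. The plan's own figure.** Inputs from Sections 8.1 and 8.2: 40% against 80%, two-sided 5%, 80% power, 10% drop-out. With pooled variance and no continuity correction:

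n = [1.960 × √(2 × 0.6 × 0.4) + 0.842 × √(0.4 × 0.6 + 0.8 × 0.2)]² / 0.4² = 22.3, so 23 per arm and 46 in total.

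46 / 0.9 = 51.1, rounded up to 52. The stated 23, 46 and 52 reproduce. Nothing in this point changes them, because 52 counts positive-histology patients only.

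**2. Follow-up under each reading, for one dosed patient with negative histology.**

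| Reading | Systematic safety observation | Days missing of 90 |
|---|---|---|
| 7.5 applies | 90 days | 0 |
| 10.2 applies | 28 days | 90 − 28 = 62 (69%) |
| 1.7 alone | not stated | not determinable |
| 3.6 or 8.1 alone | not stated | not determinable |

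**3. How many patients.** The documents give no negative-histology rate q, so 5%, 10% and 20% are assumed.

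- Extra dosed patients: m = 52/(1 − q) − 52.
- Share on canakinumab: m/2, from the 1:1 allocation.
- Share of 90-day person-time unobserved under the 28-day rule: 62m / [90 × (52 + m)], which simplifies to q × 62/90.

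| q (assumed) | Extra dosed | On canakinumab | Person-time unobserved |
|---|---|---|---|
| 5% | 2.7 | 1.4 | 3.4% |
| 10% | 5.8 | 2.9 | 6.9% |
| 20% | 13.0 | 6.5 | 13.8% |

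Worked at 10%: 52/0.9 − 52 = 5.8, and 5.78 × 62 = 358 of 57.8 × 90 = 5,200 patient-days, which is 6.9%.

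**4. What that could mean in events (illustration only).** With a constant hazard and 90-day risk r, the chance of an event between Days 29 and 90 is (1 − r)^(28/90) − (1 − r).

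- At r = 22%, the 90-day mortality given in Section 2.5 for MELD ≤ 27, this is 0.146 per patient. That is 0.4, 0.8 and 1.9 expected deaths outside the window for q = 5%, 10% and 20%.
- At an assumed r = 5% it is 0.034 per patient, or 0.1, 0.2 and 0.4 deaths.
- If all these patients stayed in a simple 90-day proportion with none of those deaths recorded, a true 22% would be understated by q × 0.146, that is 0.7, 1.5 and 2.9 percentage points.

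The risk in patients who meet the clinical criteria but have negative histology is not given and may differ from either figure.

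**The case against.** **Withdrawn does not mean that data collection stops.** A reader might join 3.6 and 8.1 to 10.1 and infer that no further data are collected on these patients. The documents do not support that. Section 10.1 confines its rule to its three sub-sections, and 10.1.1 ties withdrawal to consent. Negative histology is handled in 10.2, among patients not lost, with an instruction to follow them for safety, and 1.7 agrees. The two shorter statements leave follow-up out but do not forbid it. This objection stands, and what remains is a misleading word.

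**7.5 is not a rule for this group.** It is a general sentence, and 10.2 is the only text that gives negative-histology patients a duration. Reading 10.2 as a deliberate exception is reasonable. But neither section says so, 7.5 calls its 90 days a minimum, and 10.2 cites the schedule as its authority. The conflict stays open.

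**Later events are still captured.** Section 9.5 covers deaths and adverse events after discontinuation that may reasonably be related to the study. It would be wrong to infer that 90-day safety will necessarily miss these patients. However, capture that depends on a causality judgement cannot give complete 90-day counts of mortality, infection or kidney injury.

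**The denominator bias is conditional.** Nothing in the text says that these patients enter simple proportions, or that they are left out of safety. That choice belongs to the analysis plan still to be written. This also stands.

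**The comparison between arms is probably little affected.** With blinded 1:1 allocation the gap should be balanced on average. The harm is mainly to absolute rates and to complete accounting for exposure.

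**Conclusion.** The inconsistency is real, and its consequence is conditional. Under 7.5 nothing is lost. Under the 28-day rule in 10.2, 62 of 90 days are not systematically observed for each dosed patient with negative histology, and 90-day mortality, infection and acute kidney injury may be incomplete for them.

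At an assumed 5–20% negative rate this concerns about 3–13 patients, roughly half on canakinumab, and about 3–14% of 90-day person-time. Those figures assume exactly 52 positive-histology patients and full 90-day follow-up of everyone else. The primary endpoint and the sample size are untouched. The point should be settled before the analysis plan is written. It concerns completeness of safety data and does not undermine the trial.

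**What to change.** Reconcile Sections 1.7, 3.6, 7.5, 8.1 and 10.2 into one safety follow-up rule for dosed patients with negative histology:

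1. In 3.6 and 8.1, replace *withdrawn* with *discontinued from study treatment and the efficacy analysis*, so that the word keeps its consent meaning from 10.1.1.
2. In the statistical analysis plan, define the safety population as every dosed patient, whatever the histology.
3. State which of two routes applies:
   - collect safety and vital status over 90 days for these patients, by contact or from records, consistent with 7.5; or
   - if 28 days is a deliberate exception, say so in 7.5, censor these patients at their last safety contact, and report 90-day safety with time-to-event estimates instead of simple proportions.

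Either route gives a usable analysis, and the sponsor should decide which was intended. The second assumes that stopping at Day 28 carries no information about later risk. Because these patients are selected on histology, reporting them separately as well would let readers judge that.

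The cost is a wording amendment and, under the first route, a few extra contacts or record checks. The sample size does not change.

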11. END OF THE CLINICAL TRIAL

The recruitment period of the trial will be stopped when:

- The stated number of patients to be recruited and randomised is reached, or the trial is stopped for another reason, e.g. by the funding body or the regulatory authority.

The active treatment phase will be completed:

- 28 days after start of treatment of the last patient randomised.

The end of the trial is defined as:

- The end of the trial will occur when the final participant has completed the last study visit and all study data have been captured on the study database.

Regardless of the reason for termination, all data available for the patient at the time of discontinuation of follow-up must be recorded in the CRF. All reasons for discontinuation of treatment must be documented.

In terminating the study, the Sponsor and the Investigators will ensure that adequate consideration is given to the protection of the patient's interests.

12 REGULATORY, ETHICAL AND LEGAL ISSUES

12.1 Treatment

12.1.1 Investigational Medicinal Product Details

| Drug Name | Dosage | Description |
|-------------|-------------------------|---|
| Canakinumab | 3mg Canakinumab per kg. | Canakinumab will be made up by dilution in 100ml 5% dextrose and administered intravenously |
| Placebo | 100ml 5% Dextrose | Dextrose alone will be administered intravenously |

12.1.2 Labelling, storage and dispensing

IMP (Canakinumab) is manufactured by Novartis according to Good Manufacturing Practices (GMP) and will be packaged/stored/transported as per requirements specified in SmPC. IMP (Canakinumab) will be provided by Novartis for the trial. Labelling, storage and distribution of drug to sites will be carried out by a company independent of the funder and Sponsor. They will be contracted by Imperial College to receive the study drug from Novartis, to label and repackage the drug for clinical trial use, for final QP release and to distribute the drugs to sites as requested by the trial team.

A single dose of 3 mg/kg Canakinumab or identical placebo will be administered intravenously at baseline (Day 1). Canakinumab will be made up by dilution in 100 ml 5% Dextrose by an unblinded research personnel at each site.

The trial team at each site will randomise each new patient on the study eCRF/InForm database. This will provide a code to the trial team for that patient (that does not identify the treatment allocation) and the code will be used by the site pharmacy to identify if the patient will have active drug or placebo based on a pre specified randomisation list that pharmacy will be provided with. This will be double checked by a second pharmacist against the code on InForm and the code on the randomisation list to reduce the risk of error. The pharmacist will then either prepare the i.v. infusion bag at trial pharmacy or dispense the IMP+Placebo/Placebo-only to a designated unblinded research member who will then make up the i.v. infusion bag and label it with this code – this will be double checked by another unblinded member of the research team before administration by a blinded nurse/doctor. Patients with moderate to severe ascites should undergo large volume paracentesis prior to administration of Canakinumab.

Patients with AST >2 x ULN on Day 28 will receive a second dose of 3 mg/kg study drug administered i.v. on Day 28:

- Patients who received placebo on baseline will receive placebo.
- Patients who received canakinumab on baseline will receive canakinumab.

Overdose of IMP should be reported immediately and recorded as a protocol deviation and AE on the InForm database and the patient followed up. Reported experience with overdose of IMP is limited. In early clinical trials, patients and healthy volunteers received doses as high as 10 mg/kg, administered intravenously or subcutaneously, without evidence of acute toxicity.

12.1.3 Accountability

Hospital pharmacies will be responsible for recording study drugs dispensed. Preparation of all drug solution for injection will be recorded on the study drug accountability logs, and drug administration in the patient's medical file. The study drug stores will include a sheet recording the use of each vial of active drug. Used vials will be checked for reconciliation by the Trial Monitor at monitoring visits before destruction. At the end of the study any remaining unused vials of drug will be destroyed.

12.2 Declaration of Helsinki

The investigator will ensure that this study is conducted in full conformity with the 7th revision of the 1964 Declaration of Helsinki.

12.3 Good Clinical Practice

The study will be conducted in accordance with the guidelines laid down by the International Conference on Harmonisation for Good Clinical Practice (ICH GCP E6 R2 guidelines).

12.4 Independent Ethics Committee Approval

(vi) Initial Approval

Prior to the enrolment of subjects, the REC must provide written approval of the conduct of the study at named sites, the protocol and any amendments, the Subject Information Sheet and Consent Form and any other written information that will be provided to the subjects.

(vii) Approval of Amendments

Proposed amendments to the protocol and aforementioned documents must be submitted to the REC for approval as instructed by the Sponsor. Amendments requiring REC approval may be implemented only after a copy of the REC's approval letter has been obtained.

Amendments that are intended to eliminate an apparent immediate hazard to subjects may be implemented prior to receiving Sponsor or REC approval. However, in this case, approval must be obtained as soon as possible after implementation.

(iii) Annual Progress Reports

The REC will be sent annual progress reports in accordance with national requirements.

(iv) Annual Safety Reports and End of Trial Notification

The REC will be sent annual safety updates in order to facilitate their continuing review of the study (reference. ICH GCP E6 Section 3.1.4) and will also be informed about the end of the trial, within the required timelines.

